## 5.2 Study Medications

Within 5 calendar days following randomization, the patient should receive the first dose of study treatment. Table 1 provides the timing of study drug administration.

Patients will be treated for approximately 1 year (maximum of 17 cycles for Arm A and 13 cycles for Arm B) or until disease recurrence, death, unacceptable toxicity, symptomatic deterioration, decision by investigator to discontinue treatment, decision by patient to discontinue treatment or withdraw consent from the study, patient is lost to follow-up, or decision by Sponsor to terminate the trial, whichever is earlier.

**Table 1 Tumor Tissue Collection Schedule**

Treatment Arm	Study Treatment	Starting Dose	Frequency of Administration	Route of Administration
Arm A a	Bempegaldesleukin	0.006 mg/kg b	q3w	IV
	Nivolumab	360 mg or 4.5 mg/kg if < 40 kg c	q3w	IV
Arm B	Nivolumab	480 mg or 6.0 mg/kg if < 40 kg c	q4w	IV

IV = intravenous; q3w = every 3 weeks; q4w = every 4 weeks.

a. Bempegaldesleukin dose is based on IL-2 content. Bempegaldesleukin will be administered before nivolumab. Nivolumab administration should start at least 30 minutes from the end of bempegaldesleukin administration.

b. Bempegaldesleukin may be held or reduced to 0.003 mg/kg based on observed treatment-related toxicities. If the bempegaldesleukin dose is reduced to 0.003 mg/kg, the dose should remain at this level throughout the remainder of the study and cannot be re-escalated.

c. The lower dose is for patients who are < 40 kg. Nivolumab may be held based on observed treatment-related toxicities; no dose adjustments for treatment-related toxicities are allowed

### 5.2.1 Arm A: Bempegaldesleukin Dosing

Each patient's bempegaldesleukin (NKTR-214) dose will be determined by the patient's weight in kilograms, which will be determined before the start of each cycle. If the patient's weight is within 10% of the Cycle 1 Day 1 weight, the study drug doses do not need to be recalculated depending on institutional guidelines/preference. If the patient's weight has changed more than 10% from the Cycle 1 Day 1 weight, the dose of bempegaldesleukin must be recalculated and subsequent weight measurements should be compared with this new baseline weight to determine if further bempegaldesleukin dose recalculations are necessary.

Bempegaldesleukin (NKTR-214) will be administered before Nivolumab. Bempegaldesleukin will be administered as an IV infusion over approximately 30 minutes (exclusive of the flush time) at a starting dose of 0.006 mg/kg q3w ( $\pm$  3 days). After the bempegaldesleukin IV infusion is administered, flush the IV line with an appropriate amount of diluent (e.g., 0.9% Sodium Chloride or 5% Dextrose in Water) to ensure that the complete dose is administered. Nivolumab administration should start at least 30 minutes from the end of the bempegaldesleukin administration. Patients may be dosed no less than 18 days from the previous dose.

Bempegaldesleukin treatment can continue for patients randomized to the bempegaldesleukin and nivolumab combination arm if nivolumab is permanently discontinued due to toxicities.

### 5.2.2 Arm A and Arm B: Nivolumab Dosing

Patients in Arm A should receive nivolumab at a dose of 360 mg (or 4.5 mg/kg for patients < 40 kg) over an approximately 30-minute IV infusion on Day 1 of each treatment cycle q3w ( $\pm$  3 days). If needed, flush the IV line with an appropriate amount of diluent (e.g., 0.9% Sodium Chloride or 5% Dextrose in Water) after the nivolumab infusion. Nivolumab should be given at least 30 minutes after the completion of the bempegaldesleukin infusion.

Patients in Arm B should receive nivolumab at a dose of 480 mg (or 6.0 mg/kg for patients < 40 kg) as an IV infusion on Day 1 of each treatment cycle q4w ( $\pm$  3 days). Nivolumab should be infused over approximately 30 or 60 minutes, according to the recommended infusion time specified in the approved country-specific nivolumab label. If needed, flush the IV line with an appropriate amount of diluent (e.g., 0.9% Sodium Chloride or 5% Dextrose in Water) after the nivolumab infusion.

For patients < 40 kg, nivolumab dosing will be determined by the patient's weight in kilograms, which will be determined before the start of each cycle. If the patient's weight is within 10% of the Cycle 1 Day 1 weight, the study drug doses do not need to be recalculated depending on institutional guidelines/preference. If the patient's weight has changed > 10% from the Cycle 1 Day 1 weight, the dose of nivolumab must be recalculated and subsequent weight measurements should be compared with this new baseline weight to determine if further nivolumab dose recalculations are necessary.

Note: If a patient's weight fluctuates throughout the course of treatment, administer nivolumab based on the patient's weight at time of dosing. For example, if the patient's baseline weight is 42 kg, the patient will be dosed with 480 mg of nivolumab if the patient is on Arm B. At a later subsequent cycle, if the patient's weight falls to 38 kg, the patient will be administered 6.0 mg/kg.

There will be no dose escalations or reductions of nivolumab allowed; however, dose modification due to weight change will be allowed. In Arm A, patients may be dosed no less than 18 days from the previous dose during q3w cycles. In Arm B, patients may be dosed no less than 25 days from the previous dose during q4w cycles.

Doses of nivolumab may be interrupted, delayed, or discontinued depending on how well the patient tolerates the treatment. In the event that bempegaldesleukin is permanently discontinued due to toxicities, patients may continue on nivolumab alone.

### **5.3 Pharmacokinetic (PK) and Immunogenicity Measurements**

Only limited plasma PK samples for NKTR-214-RC were analyzed before study termination, all other PK and immunogenicity sample assessments as described in study protocol were not performed due to early study termination.

## 6.0 STATISTICAL CONSIDERATIONS

### 6.1 General Considerations

Summary statistics for continuous variables will include the mean, standard deviation, median, minimum, and maximum. The mean and median will be presented to one decimal place beyond which the data were captured. The standard deviation will be presented to two decimal places beyond which the data were captured. The minimum and maximum will be presented to the precision with which the data were captured.

Categorical variables will be presented as frequency counts and percentages. A row or column denoted 'Missing' will be included in count tabulations where necessary to account for dropouts and missing values. Percentages will be rounded to 1 decimal place and the percent will be suppressed when the count is zero. The denominator will be the number of patients in the population of interest unless otherwise noted.

Data listings will be created to support each table and to present all data. Data listings will be presented by treatment group and patient number.

### 6.2 Determination of Sample Size

Up to 950 Stage III/IV melanoma patients at high risk of recurrence will be randomized into the two arms (N plus nivolumab vs. nivolumab) in a 1:1 ratio. Enrollment of 950 patients is estimated to take approximately 22.5 months, assuming an enrollment rate of 50 patients/month, with a 7-month of ramp-up.

The sample size is calculated to power the comparison of RFS between the two treatment arms. Based on the RFS results for nivolumab from Bristol-Meyers Squibb study CheckMate-238, a non-constant RFS hazard was observed. Thus, for sample size calculation, a piecewise exponential distribution was assumed in each treatment arm with a constant hazard ratio of 0.7. Specifically, in the nivolumab arm, four different hazard rates were assumed before 3 months, between 3 and 12 months, between 12 and 24 months, and after 24 months, corresponding to RFS rates of 90%, 70.5%, 62%, and 51.7% at 3, 12, 24, and 48 months, respectively. At a two-sided overall alpha level of 0.05, a total of 400 RFS events are needed to detect a hazard ratio of 0.7 with 94% power. The final analysis will occur if 400 events are observed or a minimum follow-up of 45 months is reached, whichever occurs first. Given an enrollment period of 22.5 months, minimum follow-up of 45 months, and a 5% annual dropout rate, a total sample size of 950 patients (475 per treatment arm) is required to observe the needed 400 RFS events at 68 months from first patient first visit (FPFV) for final analysis. It is projected that an observed hazard ratio of 0.811 or less would result in a statistically significant improvement in the final analysis of RFS.

A group sequential testing procedure will be employed with two interim analyses at approximately 320 events (80% of the targeted RFS events for final analysis) are observed, which is expected to be 42 months from FPFV, and 360 events (90% of the targeted RFS events for final analysis) are observed, which is expected to be 54 months from FPFV. The O'Brien and Fleming boundaries will be utilized in this analysis for the rejection of null hypothesis to maintain an overall nominal significance level of 0.05 (two-sided). The boundary values for the rejection of null hypothesis are given in [Table 2](#).

The secondary endpoint of OS will be tested hierarchically given the significance of RFS.

**Table 2 Formal Interim Analyses for RFS**

Analyses	No. of Events	Time (Month) from FPFV	Critical P-value (2-sided)	Critical HR
1st interim analysis	320	42	0.0244	0.776
2nd interim analysis	360	54	0.0295	0.793
Final analysis	400	68	0.0383	0.811

FPFV = first patient first visit; HR = hazard ratio; No. = number; RFS = recurrence-free survival.

### 6.3 Analysis Populations

**Safety Population:** All patients who receive at least 1 dose (or partial dose) of study drug. Patients are grouped according to the treatment they actually received.

Due to early termination of this study, all analyses in this SAP will be performed on Safety Population.

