9.0 STATISTICAL PLAN

9.1 General Considerations

In general, continuous data will be summarized by descriptive statistics, including number of patients, mean, standard deviation, median, minimum, and maximum. Categorical data will be summarized by the number and percentage of patients. Unless otherwise specified, data will be summarized by treatment arm.

All efficacy endpoints will be analyzed using the ITT population. All safety endpoints will be summarized using the safety population.

A detailed description of analysis methods will be provided in the statistical analysis plan (SAP). The potential impact of COVID-19 on this trial will be assessed. Any changes to the analyses that are required due to COVID-19 will be detailed in the SAP.

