9.3 Analysis Sets

For the purposes of analysis, the following populations are defined in [Table 13](#).

Table 13: Analysis Populations

Population	Description
ITT Population	All patients who are randomized. Patients are grouped within the ITT population according to the treatment to which they are randomized. This is the primary analysis set for baseline characteristics and efficacy endpoints.
Safety Population	All patients who receive at least 1 dose (or partial dose) of study drug. Patients are grouped according to the treatment they actually received. This is the primary analysis set for all safety analyses and drug administration.
PK Population	All patients in the safety population who have evaluable analyte concentration-time profiles that allow for computation of meaningful PK parameter values.
Immunogenicity Population	All treated patients with baseline and at least 1 post-baseline immunogenicity assessment.
Biomarker Population	All randomized patients who have biomarker data available at baseline. For pharmacodynamic biomarkers, the biomarker population includes all randomized patients who have baseline and at least one post-baseline biomarker data available.
HRQoL Population	All patients in the ITT population who had a baseline and at least 1 post-baseline assessment (defined for each instrument).

HRQoL = health-related quality of life; ITT = intent-to-treat; PK = pharmacokinetic.

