9.4.2 Secondary Endpoints

Secondary endpoints are presented in [Table 15](#).

Table 15: Secondary Endpoints

Endpoint	Description
OS	Defined as the time between the date of randomization and the date of death due to any cause. Patients who do not have a date of death will be censored on the last date for which a patient was known to be alive. Evaluated in the ITT population.
DMFS by BICR	Defined as the time between the date of randomization and the date of first distant metastasis by BICR or date of death due to any cause, whichever occurs first. For patients who remain alive and distant metastasis-free, DMFS will be censored on the date of last disease assessment. DMFS will be evaluated in patients who are Stage III at study entry.
DMFS by Investigator	Defined as the time between the date of randomization and the date of first distant metastasis by Investigator or date of death due to any cause, whichever occurs first. For patients who remain alive and distant metastasis-free, DMFS will be censored on the date of last disease assessment. DMFS will be evaluated in patients who are Stage III at study entry.
PFS2	PFS2 is defined as time from randomization to progression per Investigator after the start of next line of therapy or death, whichever occurs first. Patients who were alive and without progression after the next line of therapy can be censored at last known alive date. Evaluated in the ITT population. Details on the PFS2 analysis will be described in the SAP.
Overall Safety and Tolerability	Measured by the incidence of adverse events, serious adverse events, deaths, and laboratory abnormalities in the safety population.

Table 15: Secondary Endpoints (Cont'd)

Endpoint	Description
PROs	Measured by (group-level and individual-level) changes from baseline in scores for the GH/QoL and physical functioning subscales of the EORTC QLQ-C30 questionnaire.
PD-L1 Expression as a Predictive Biomarker for RFS	Measured by the RFS by BICR endpoints based on PD-L1 expression level.
RFS by Investigator	Defined similar to the primary endpoint, but recurrence and new primary melanoma are decided by Investigator.

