9.6.2 Secondary Analyses

Only RFS by BICR and OS are formally tested with an overall type I error controlled at 0.05 level via closed sequential testing procedure. If RFS by BICR is statistically significant at any of the planned analyses, the OS endpoint will be tested at 0.05 alpha level when the follow-up time is at least 5 years for all patients.

The secondary analysis of OS in the ITT population will be conducted using a two-sided log-rank test stratified by randomization stratification factors only if the primary analysis of RFS claims significance. A stratified Cox proportional hazards model with treatment as the single covariate will be used to estimate the hazard ratio and corresponding 95% CI. The Kaplan-Meier method will be used to further summarize OS, including Kaplan-Meier curves, medians with corresponding 95% CIs, and OS rates at 6, 12, 18, 24, and every 12 months thereafter with 95% CIs.

To calculate power for the OS comparison, a piecewise exponential distribution can be assumed in each treatment arm with a constant hazard ratio of 0.75. Specifically, in the nivolumab arm, three different hazard rates are assumed before 3 months, between 3 and 36 months, and after 36 months, corresponding to OS rates of 99%, 75%, and 65% at 3, 36, and 60 months, respectively.

The OS endpoint will be tested at a two-sided alpha level of 0.05 only if RFS by BICR is statistically significant at any of the planned analyses and when all patients have the minimum 5-year follow-up, regardless of the number of OS events observed by then. This OS analysis is projected to occur at 83 months from the first patient randomized (~23 months of accrual and 60 months of follow-up based on current enrollment assumptions). Approximately 330 OS events are expected to be observed by then, which will provide 74% power to detect a hazard

ratio of 0.75. The critical hazard ratio is 0.806 if exactly 330 OS events are observed at the time of analysis. The standard Kaplan-Meier estimate and Cox regression model will be used to analyze the OS endpoint.

Under the current enrollment assumptions, it is expected that 177, 229, and 277 OS events will be observed at the first and second interim and the final RFS analysis at 42 months, 54 months, and 68 months from the first patient randomized, respectively.

Other secondary [REDACTED] endpoints will be analyzed similarly to OS. Details of these secondary analyses will be described in the SAP.

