To evaluate PD-L1 expression as a predictive biomarker, a Cox proportional hazards model will be used to test the interaction between PD-L1 expression ($\geq 1\%$ vs $< 1\%$) and treatment arm for the RFS endpoints. Additionally, RFS will be analyzed within each PD-L1 expression subgroup ($\geq 1\%$ vs $< 1\%$) including log-rank tests and hazard ratios with corresponding CIs. The Kaplan-Meier method will be used to further summarize RFS, including Kaplan-Meier curves, medians and 95% CIs, and RFS rates in each subgroup at 6, 12, 18, 24, and every 12 months thereafter with 95% CIs. The analyses will be descriptive.

The analysis of EORTC QLQ-C30 data will be performed in the HRQoL population (defined in Section 9.3). Scores for all EORTC QLQ-C30 items and subscales will be linearly transformed to a 0 to 100 metric where higher values indicate better functioning/well-being or lower symptom burden (see EORTC QLQ-C30 Scoring Manual). The primary domains of interest for the HRQoL analysis are GH/QoL and physical functioning of EORTC QLQ-C30.

Scores and post-baseline mean score changes and percent of subjects' HRQoL response status (e.g., improved, worsened, no change) compared to their baseline for the EORTC QLQ-C30 primary subscales will be summarized (e.g., mean with standard deviation and 95% CI, median, minimum, maximum) by treatment group and assessment time point. The clinically meaningful change for group-level analysis will be defined for each EORTC QLQ-30 domain as recommended by the literature (Musoro, 2018), specifically as 7 for GH/QoL and 5 for physical functioning. For individual-level analysis (i.e., percent of subjects who achieved the HRQoL change), the clinically meaningful change thresholds will be defined as 5 (-5) for improvement (deterioration) for both GH/QoL and physical functioning (Cocks, 2015).

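### SAP 6.3 moves baseline, efficacy and PRO analyses from the protocol's ITT-based sets to the as-treated Safety Population, and early termination does not explain the move

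*SAP*

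**What the plan says.** **Protocol.** Section 9.1 gives a general rule: "All efficacy endpoints will be analyzed using the ITT population". Table 13 in Section 9.3 defines ITT as all randomised patients in their assigned arm and adds: "This is the primary analysis set for baseline characteristics and efficacy endpoints". Table 15 in Section 9.4.2 repeats the rule for OS and PFS2 ("Evaluated in the ITT population"), and Section 9.6.2 repeats it for OS: "The secondary analysis of OS in the ITT population will be conducted using a two-sided log-rank test". DMFS is limited to patients who are Stage III at entry. For PROs, Table 13 defines an HRQoL set as ITT patients with a baseline and at least one later assessment on the instrument, and Section 9.6.2 assigns the QLQ-C30 analysis to it.

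**SAP.** Section 6.3 defines one population only, patients with at least a partial dose: "Patients are grouped according to the treatment they actually received". It then applies that population to everything: "Due to early termination of this study, all analyses in this SAP will be performed on Safety Population". Later sections repeat it for demographics (6.9.1), stratification factors (6.9.2), OS (6.11.2.1), investigator DMFS (6.11.2.2), PFS2 (6.11.2.3), PROs (6.11.2.5) and investigator RFS (6.11.2.6).

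**The concern.** The SAP changes who is counted and which arm they are counted in. Patients randomised but never dosed drop out, and anyone given the other arm's treatment changes group. The by-arm estimates then no longer describe the groups that randomisation formed.

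SAP 6.11 drops every comparison between arms, so type I error and power are not at stake. What is at stake is how the by-arm tables are read. They will be set side by side as if they described the randomised arms. The trial is open-label, so failing to start treatment can depend on the arm assigned. First dose is due within 5 days of randomisation, which limits this, but the exposure table in SAP 6.10.2 has categories running beyond 21 days.

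**Working it through.** **1. Population by analysis**

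| Analysis | Protocol | SAP |
|---|---|---|
| Baseline | ITT (9.3) | Safety (6.9.1) |
| Strata | ITT, as a baseline characteristic (9.3) | Safety (6.9.2) |
| OS | ITT (9.1, 9.4.2, 9.6.2) | Safety (6.11.2.1) |
| RFS, investigator | ITT (9.1) | Safety (6.11.2.6) |
| DMFS, investigator | ITT, Stage III subset (9.1, 9.4.2) | Safety, Stage III subset (6.11.2.2) |
| PFS2 | ITT (9.1, 9.4.2) | Safety (6.11.2.3) |
| QLQ-C30 | HRQoL subset of ITT (9.3, 9.6.2) | Safety (6.11.2.5) |

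**2. Does termination force the change?** An ITT analysis needs the randomisation date, the assigned arm and whatever follow-up exists.
- SAP 6.8 still counts randomised patients by arm, and 6.9.2 counts them by country. Read literally, both conflict with the blanket rule in 6.3.
- OS, RFS, DMFS and PFS2 all still start at randomisation.
- The OS and RFS rules already censor patients without follow-up or assessment at randomisation.
- SAP 3.0 and 4.0 list what termination alters. Neither mentions the population.

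**3. What the planned tables reveal.** For arm A, randomised N minus Safety N equals the undosed patients in A plus the net movement from A to B through wrong-arm dosing. Movements cancel in the total, so the overall undosed count can be recovered. The by-arm count cannot.

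**4. Size.** No figure in the plan depends on this point, and the documents give no undosed or wrong-arm count. The following is an illustration under stated assumptions.

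*Assumptions.* 774 randomised (SAP 5.1 says about 774 enrolled, which may not be the same thing); 387 per arm; 1–3% undosed; undosed patients differ from dosed patients by 10–20 percentage points in 12-month RFS. The reference rate is the design value for nivolumab, 70.5% (Protocol 9.2).

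- Undosed patients: 774 × 0.01 = 7.7, about 8; 774 × 0.03 = 23.2, about 23.
- Shift in an arm's estimate = undosed fraction × difference.
  - Spread evenly: 1% × 10 = 0.1 points to 3% × 20 = 0.6 points.
  - All in one arm: 8/387 = 2.1%, × 10 = 0.2 points; 23/387 = 5.9%, × 20 = 1.2 points.
- Wider case: 5% of an arm undosed with 12-month RFS of 40% gives 5% × (70.5 − 40) = 1.5 points.
- If no undosed patient is followed, all are censored at day 0 and no Kaplan-Meier curve moves. Only N and crude percentages change: a crude event percentage of 29.5% (100 − 70.5) becomes 29.5 × 0.99 = 29.2% or 29.5 × 0.97 = 28.6%.

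*Standard error for comparison* (complete follow-up, hence a minimum):
- RFS: √(0.705 × 0.295 / 387) = 2.3 points.
- OS, from the Protocol 9.6.2 nivolumab rates of 99% at 3 months and 75% at 36 months: hazard = −ln(0.75/0.99)/33 = 0.00841 per month; 12-month OS = 0.99 × exp(−0.00841 × 9) = 91.8%; SE = √(0.918 × 0.082 / 387) = 1.4 points.

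**The case against.** The strongest reply is one of proportion. The main purpose of ITT is to protect a randomised comparison, and none is made. The largest one-arm shift, 1.2 points, needs 3% undosed, all in one arm, all followed and all 20 points different, and is still about half the minimum standard error. This stands, and it is why the point is modest.

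A second reply is that the SAP discloses the change and gives a reason, and a link to termination is conceivable. If accrual was running at the planned 50 a month, about 8 patients (50 × 5/30.4) would be between randomisation and first dose at any moment. Patients left undosed by the closure would not be arm-selective and, without follow-up, would add nothing to the curves. The documents do not say this happened. If it did, it would be a reason to report those patients, not to remove them from the defined set.

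Third, the PRO change has little practical effect. The HRQoL set already requires a post-baseline questionnaire, and questionnaires are scheduled around dosing or timed from the last dose, so few undosed patients could enter it. The SAP set is in one respect broader, because it drops that requirement. The contradiction in the text remains, but few scores would move.

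Fourth, wrong-arm dosing is undocumented, randomisation and supply run through the IRT, and patient listings might allow undosed and misdosed patients to be told apart. That is fair, but readers of the summary tables could not do so.

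Fifth, the gap in the DMFS censoring rule also affects dosed patients. True, but restoring ITT makes it matter: an undosed patient with no later scan has only the screening assessment, which can precede randomisation.

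**Conclusion.** The concern holds. The SAP departs from the protocol's analysis set for baseline, strata, four time-to-event endpoints and PROs, and the only reason it gives does not account for excluding or regrouping randomised patients. The contradiction follows from the text and needs no assumption.

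The numerical effect is probably small and cannot be determined from the documents. Across the illustrated cases the shift in 12-month RFS runs from zero to 1.5 points, always below the minimum standard error of 2.3. This rests on assumed undosed fractions, assumed differences in outcome, and treating 774 as the number randomised. That last step is uncertain, because the protocol uses enrolment both for entry to screening (5.2) and for the patients to be randomised (9.2). The effect of any wrong-arm dosing was not estimated. The change should be made because it restores the protocol's own rule at little cost, not because a large distortion is expected.

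**What to change.** - In SAP 6.3, define ITT (all randomised, by assigned arm) and use it for baseline and strata (6.9), OS (6.11.2.1), investigator DMFS in the Stage III subset (6.11.2.2), PFS2 (6.11.2.3) and investigator RFS (6.11.2.6).
- Use the protocol's HRQoL subset of ITT for PROs (6.11.2.5).
- Add one sentence to the DMFS rule: patients alive with no post-randomisation assessment are censored at randomisation, matching the RFS rule.
- Keep the Safety Population for exposure and adverse events, and remove the blanket statement in 6.3.
- In 6.8, report by arm the number randomised but not dosed and the number given a treatment other than the one assigned.

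All results stay descriptive. The cost is a population and arm flag for these analyses, one censoring sentence and two disposition rows. OS and RFS need no new rule, and no new data are collected.
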